10.0 MODIFIED FOLLOW-UP AND OFF STUDY CRITERIA

10.1 Criteria for Modified Follow-Up

The following criteria will result in the patient being ineligible for further treatment on the protocol, although response data will continue to be collected as applicable.

- 10.1.1 Any patient who develops grade \geq III infusional and/or organ toxicity that is NOT (1) pre-existing, or (2) due to infection or (3) due to underlying malignancy and is considered to be possibly, probably, or definitely related to the study drug. In such patients, the toxicities will be followed until resolution or their off-study date. Although no toxicity has been associated with the infusion of this product in patients with Hodgkin and non-Hodgkin lymphoma, we will actively look for evidence of any adverse events, such as cytokine release syndrome.
- 10.1.2 Any patient who receives any other hematopoietic progenitor cell product. In such patients, adverse event data collection will cease.
- 10.1.3 Any patient who receives therapy for progression of their breast cancer. In such patients, adverse event data collection will cease.
- 10.1.4 Any patient who desires to withdraw from the study or if the physician feels that it is in the best interest of the patient, treatment will be discontinued.

Patients who meet modified follow-up criteria remain on long-term follow-up as per the Summary of Monitoring (see table in Section 7.3.1)

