5.2 Administration and Monitoring

Patients will be evaluated in the clinic and 2 fixed doses of CTL will be administered 4 weeks apart. Patients will be monitored for clinical toxicity by the CTEP NCI Common Toxicity Criteria Scale (Version 4.X, See Section 13.3) with the exception of CRS toxicities that are related to T-cell infusions. CRS toxicities will be graded according to Appendix I. We will also analyze immunological parameters including phenotype and CTL frequencies by ELISpot and tetramer studies in patients who have HLA types for which tetramers are available. This information will be used to determine the in vivo persistence of the infused product and whether multiTAA-specific T cells will be able to recruit the patient's endogenous immune system as measured by epitope spreading. Functional analyses (antigen-specific cytotoxicity and cytokine release) will be performed by chromium release assays and ELISpot/intracellular cytokine staining, respectively. The levels of serum cytokines before and following infusion will be compared. If needed, we will compare the infused product with the patient's peripheral blood using TCR deep-sequencing. A time period of 6 weeks post the 2nd infusion will constitute the time for clinical efficacy and safety monitoring. If patients have had a partial response or have stable disease they will be eligible to receive up to 6 further doses of CTLs, each of which will consist of the same cell dose or less (if there is not enough product available for the subject's original dose) than their second infusion

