To obtain preliminary data on the clinical efficacy and safety monitoring, patients will be monitored for 6 weeks after the final injection for toxicity using standard NIH criteria. If a patient develops Grade III-IV toxicity attributable to the CTL infusions at any time during the extended dosing regimen, they will not be able to receive any more CTL infusions.

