9.3 Analysis Set

Evaluable for response: Only patients who receive both infusions will be evaluable for response.

Evaluable for adverse events: All patients who received the first infusion will be evaluable for adverse events.

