9.4 Stopping Rule

If there are 2 patients with grade 4 events considered possibly related to the study drug, the study will be halted for review by the Data Safety Monitoring Committee and the FDA.

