12.0 REPORTING REQUIREMENTS

- 12.1 Register all patients with the research nurse/research coordinator.
- 12.2 Enter all patients by phoning [name]. The following data will be captured:

- Eligibility
- Pre-study
- Concomitant Medication
- Adverse event
- CRS Adverse Event (if applicable)
- Off study
- Death

- 12.3 Drug Toxicity and/or Adverse Reactions

12.3.1 Toxicity Grading: The criteria listed in the CTEP (Version 4.X) of the NCI Common Toxicity Criteria Scale will be used in grading toxicity with the exception of CRS

TACTIC

Version 1.0 6/17/2016
Version 1.1 8/12/2016

Version 1.2 11/3/2016
Version 2.0 3/20/2017

Version 3.0 6/28/2017
Version 3.1 7/24/2017

Version 3.2 11/16/2017
Version 4.0 12/03/2018

Version 4.1 7/24/2019

toxicities that are related to T-cell infusions. CRS toxicities will be graded according to Appendix I.

12.3.2 The CTEP CTCAE (Version 4.X) is identified and located on the CTEP website at: http://ctep.cancer.gov/protocolDevelopment/electronic_applications/ctc.htm.

12.3.3 Adverse events will be collected as per SOP J 02.05.XX and J 02.75.XX. Data on adverse experiences/toxicities regardless of seriousness, must be collected for documentation purposes only for 6 weeks after the last dosing of study drug/biologic.

12.3.4 Serious adverse events will be collected as per SOP J 02.06.XX.

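### Sections 10.1.2 and 10.1.3 end adverse event collection when new therapy starts, 12.3.3 requires six weeks after the last dose, and toxicity and the 9.4 halt count can therefore be under-recorded

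*Combined protocol and SAP*

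**What the plan says.** Two sets of provisions govern when adverse event collection ends.

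- Section 10.1.3 lists, among the reasons for modified follow-up, "Any patient who receives therapy for progression of their breast cancer. In such patients, adverse event data collection will cease". Section 10.1.2 reads "Any patient who receives any other hematopoietic progenitor cell product. In such patients, adverse event data collection will cease". Neither refers to the time since the last infusion, or exempts serious or related events.
- Section 12.3.3 says: "Data on adverse experiences/toxicities regardless of seriousness, must be collected for documentation purposes only for 6 weeks after the last dosing of study drug/biologic". It makes no exception for new therapy. Section 9.2 agrees ("patients will be monitored for 6 weeks after the final injection for toxicity using standard NIH criteria"), as does section 5.2 ("A time period of 6 weeks post the 2nd infusion will constitute the time for clinical efficacy and safety monitoring"). Section 11 asks for adverse event records on every patient.

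The safety analysis depends on these data. Section 9.3 states "All patients who received the first infusion will be evaluable for adverse events". The study-level halt in section 9.4 applies "If there are 2 patients with grade 4 events considered possibly related to the study drug" and gives no observation window.

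Three further provisions bear on the point. Section 6.8 discourages other cancer treatment until six weeks after the second dose, but also says what happens to a patient who receives it between doses. Section 10.1.1 follows related toxicity of grade III or higher once it has been identified. Section 12.3.4 sends serious adverse events to a separate SOP, which is not part of the documents.

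**The concern.** A patient who starts treatment for progression three weeks after the last infusion falls under both rules. One ends adverse event collection that day; the other requires three more weeks. Staff could follow either and cite the protocol.

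If they follow 10.1.3, the patient stays in the safety denominator with a shortened observation period. Section 9.2 plans descriptive safety summaries and mentions no allowance for unequal follow-up. Truncation can only remove events, so any bias in the crude rates and in the 9.4 count is downward. It also falls selectively on patients who progress early. Safety is a stated purpose of the study in section 9.0, and 9.4 is the only safety trigger at study level.

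**Working it through.** **1. Where the two rules overlap.** The 12.3.3 window is 42 days from the last dose.

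- Two doses (Day 0 and Day 28): the window is Day 28 to Day 70. Section 6.8 discourages other therapy over the same period, so overlap arises only when 6.8 is not followed.
- One dose: the window is Day 0 to Day 42. Section 6.8 foresees other treatment between doses and takes the patient off treatment; 9.3 keeps the patient in the safety set.
- Additional doses (up to six, section 6.2): 12.3.3 runs from the last of them. Section 6.8 covers only the first two doses, so it does not restrict a switch here.

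**2. How much of the window is lost.** Days lost = 42 − (start day after last dose). The start days are assumed.

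| Start of new therapy | Days lost | Share of 42-day window | Share of a two-dose patient's 28 + 42 = 70 days |
|---|---|---|---|
| Day 14 | 28 | 67% | 40% |
| Day 28 | 14 | 33% | 20% |
| Day 42 or later | 0 | 0% | 0% |

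**3. The plan's own figures (section 9.1.1).** Accrual: 17 / (1 − 0.20) = 21.25, rounded up to 22. Probability of early stopping at a 5% benefit rate: 0.95^9 = 0.630. Expected size: 9 + 8 × (1 − 0.630) = 11.96. Exact enumeration of the two-stage rule gives a type I error of 0.047 and power of 0.905. All agree with the plan, and this point does not affect them. The plan gives no operating characteristics for the 9.4 rule.

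**4. Effect on the 9.4 count.** Let q be the true proportion of patients with a possibly related grade 4 event and m the share of those missed. Both are assumptions. With p = q(1 − m),

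P(at least 2 of n) = 1 − (1 − p)^n − n·p·(1 − p)^(n−1).

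Check for n = 22, q = 10%, m = 0: 1 − 0.0985 − 0.2407 = 0.661.

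| n | q | m = 0 | m = 10% | m = 25% | m = 50% |
|---|---|---|---|---|---|
| 22 | 5% | 0.302 | 0.260 | 0.199 | 0.104 |
| 22 | 10% | 0.661 | 0.601 | 0.499 | 0.302 |
| 22 | 15% | 0.863 | 0.818 | 0.726 | 0.499 |
| 17 | 10% | 0.518 | 0.460 | 0.368 | 0.208 |

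Total accrual is 22, so that is an upper bound for the number infused; 17 is shown for comparison.

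**5. What m might be.** If a share s of patients switch and each loses a fraction f of observed time, a constant event rate gives m = s × f. A two-dose patient who loses half the six-week window loses 21 of 70 days, so f = 0.30. For q = 10% and n = 22:

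- s = 10%: m = 3%, probability 0.64
- s = 30%: m = 9%, probability 0.61
- s = 50%: m = 15%, probability 0.57

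The corresponding value with no loss is 0.66. For a one-dose patient f would be 21/42 = 0.50, and m correspondingly larger.

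**The case against.** The strongest reply is that the overlap should be uncommon and its effect small. Section 6.8 discourages other therapy over exactly the window that matters for a two-dose patient. Scheduled response imaging comes at week six after the second dose, so a patient found to progress only at that scan loses nothing. Possibly related grade 4 events are also those most likely to be reported as serious under 12.3.4, and toxicity already identified under 10.1.1 is still followed. Stopping collection at new therapy may even be a deliberate exception to 12.3.3, meant to keep toxicity of the next treatment out of the record.

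Much of this stands, and it rules out several stronger readings.

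- A reader might infer from the 5% null benefit rate that most patients would switch inside the window. That rate applies at ten weeks from the first infusion, which is the end of the window, and says nothing about earlier switching.
- A reader might equate losing half the six weeks with losing half the events. For a two-dose patient it is 30% of observed time, and less of the events if toxicity clusters near infusion.
- A reader might conclude that grade 4 events after a switch are lost. That cannot be shown without the SOP.
- A reader might take 9.3 to score truncated patients as fully observed and event free. It only defines who is evaluable; events before the switch still count.

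The contradiction itself remains. Section 6.8 is worded as a recommendation, foresees departures, and is silent after additional doses. Imaging may be done earlier if clinically indicated (7.3.3), in patients whose disease is progressing at entry. Section 10.1.3 exempts nothing, and no section presents it as an exception to 12.3.3.

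**Conclusion.** The concern holds in a limited form. Sections 10.1.2 and 10.1.3 conflict with 12.3.3 for any patient who starts the named therapy within six weeks of the last infusion. For those patients non-serious events, and possibly serious ones, can go unrecorded while the patient stays in the safety denominator. Toxicity rates and the 9.4 count can then be biased low, never high. The documents do not support saying that they will be under-recorded, or that this is routine.

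The size is unknown, since neither the share switching nor the grade 4 rate is given. The probabilities above show how sensitive the halt rule would be under stated assumptions (independent patients, a common rate, and, in step 5, a constant event rate over time); they are not estimates for this trial. The primary efficacy analysis is unaffected. The change is worth making because the bias runs in one direction, concerns safety, and is cheap to remove.

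**What to change.** Reconcile 10.1.2 and 10.1.3 with 12.3.3, 12.3.4 and 9.4:

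- State that adverse event collection runs to six weeks after the last dose regardless of new therapy, and may cease after that.
- State in 12.3.4 that serious event collection over this period is likewise unaffected by new therapy.
- Record the start date of any new therapy and tabulate adverse events before and after it.
- State in 9.4 that possibly related grade 4 events anywhere in the full window count towards the halt.

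The cost is a wording amendment, one added date field and at most six more weeks of data per affected patient. Contacts at weeks 1, 2, 4 and 6 are already scheduled after the second and each additional infusion (7.1, 7.3.5). A patient who stops after one dose has no separate calendar and would need a contact near week six. Some later events will be due to the new therapy; the before-and-after tabulation makes that visible, and relatedness is still judged event by event.

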10.2 OFF STUDY

- 10.2.1 Completion of study-specified procedures.
- 10.2.2 Refusal of study follow up by patient
- 10.2.3 Lost to follow up
- 10.2.4 Death

Any questions regarding patients on this study should be addressed to [name] at [contact].

11.0 RECORDS TO BE KEPT

The research nurse/coordinator will maintain a database documenting on study information, adverse events, off study notification and death information. The dates and doses of therapy as well as clinical chemistries, hematologic parameters, the clinical status and occurrence of any adverse events and subsequent interventions are to be kept on all patients.

Imaging reports
Surgical summaries
Autopsy summaries, where appropriate
Informed consent documents

All required clinical evaluation records will be the responsibility of Principal Investigator who will also be responsible for analysis of the clinical outcome and toxicity.

The laboratory evaluation of immunological efficacy will be the responsibility of [name].

12.0 REPORTING REQUIREMENTS

- 12.1 Register all patients with the research nurse/research coordinator.
- 12.2 Enter all patients by phoning [name]. The following data will be captured:

- Eligibility
- Pre-study
- Concomitant Medication
- Adverse event
- CRS Adverse Event (if applicable)
- Off study
- Death

- 12.3 Drug Toxicity and/or Adverse Reactions

12.3.1 Toxicity Grading: The criteria listed in the CTEP (Version 4.X) of the NCI Common Toxicity Criteria Scale will be used in grading toxicity with the exception of CRS

TACTIC

Version 1.0 6/17/2016
Version 1.1 8/12/2016

Version 1.2 11/3/2016
Version 2.0 3/20/2017

Version 3.0 6/28/2017
Version 3.1 7/24/2017

Version 3.2 11/16/2017
Version 4.0 12/03/2018

Version 4.1 7/24/2019

toxicities that are related to T-cell infusions. CRS toxicities will be graded according to Appendix I.

12.3.2 The CTEP CTCAE (Version 4.X) is identified and located on the CTEP website at: http://ctep.cancer.gov/protocolDevelopment/electronic_applications/ctc.htm.

12.3.3 Adverse events will be collected as per SOP J 02.05.XX and J 02.75.XX. Data on adverse experiences/toxicities regardless of seriousness, must be collected for documentation purposes only for 6 weeks after the last dosing of study drug/biologic.

12.3.4 Serious adverse events will be collected as per SOP J 02.06.XX.

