- (iii) Shared tumor-specific TAA (e.g. the cancer testis antigens [CTA] - MAGE, BAGE, GAGE, NY-ESO-1, SSX, PRAME) are expressed in multiple tumors including breast cancer but not in healthy organs⁷⁻¹¹, with the exception of germ line tissues that are immune privileged and therefore not susceptible to T cell attack. Most CTAs have heterogeneous expression in cancer tissues and are frequently expressed in high-grade or late tumor stages, with expression often correlated with a worse prognosis. Furthermore, tumors expressing one CTA are also often found to express multiple CTAs, and several have been found to be targets of spontaneous humoral or cell-mediated immune responses¹²⁻¹⁴. Thus, CTAs are particularly attractive as targets for tumor immunotherapy since reactive T cells can be produced on a large scale to provide broad-spectrum protection against a variety of tumors. CTAs have been targeted in both vaccine and T cell therapy protocols, with evidence of clinical efficacy¹⁵⁻²¹.

- (iv) The last group of antigens are over expressed in many different tumors but expressed at low levels in healthy tissue (eg. hTERT, CEA and Survivin). T cells targeted to these antigens carry the risk of inducing collateral damage to normal tissues co-expressing the antigen (e.g. CEA and normal biliary epithelium), and there are limited clinical data available regarding the safety of targeting these antigens *in vivo*. However, Survivin- and CEA-specific T cells have been isolated from the peripheral blood of patients who have cleared their tumors, and increases in Survivin-specific T cells in patients receiving oncolytic viruses have been reported, suggesting that they can have efficacy without toxicity in patients²²⁻²⁷.

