7.0 PATIENT EVALUATION

7.1 Follow up Interval

Patients shall be seen in clinic prior to the first and second infusions and evaluated (seen in clinic or contacted by a research coordinator) at 1 -2 week intervals for up to six weeks after the 2nd infusion and then at 3, 6, 9 and 12 months (post 2nd infusion). We will then continue to follow patients clinically for up to 4 additional years (total of 5 years follow-up) to evaluate long-term disease responses. If persistence of cells is noted at the 12 month visit, additional follow-up will added. Additional visits will be obtained as clinically indicated or if the patient is having more than 2 infusions.

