7.3 Other Studies

- 7.3.1 The following investigations will be obtained at pre-infusion for CTL #1 and on days of subsequent CTL infusions

CBC and differential and Complete Metabolic Panel (CMP).

- 7.3.2 Pregnancy testing is required on female patients of childbearing potential prior to CTL infusion #1. Pregnancy testing is not required prior to CTL infusion #2 for patients treated.

- 7.3.3 Diagnostic imaging (CT scans, MRI, nuclear imaging) and/or blood tests (serum cytokines) to document measurable disease and response to therapy at pre-infusion and 6 weeks following the second infusion. The time may vary by 1-2 weeks due to scheduling issues and may be done earlier if clinically indicated. The choice of imaging will depend on what studies have been most informative in following the patient's disease. If diagnostic imaging studies are performed at other times either during or after treatment on this study, that data will be collected and information gained will be used for this study.

- 7.3.4 The following investigations will be obtained pre-infusion, and at 1, 2, 4 weeks after the first infusion and then at 1, 2, 4, 6 weeks and 3, 6, 9, and 12 months following the 2nd infusion. 20-40ml of peripheral blood will be collected in preservative-free heparin anticoagulant. This blood will be used for analysis of specificity of CTL response using HLA-peptide tetramer analysis and immune function assays including ELISpot, intracellular cytokine staining and cytotoxicity assays. Serum will be batched for analysis of blood cytokine levels. These studies will be done on patients on whom the appropriate reagents are available.

- 7.3.5 If the patient has additional injections of cells after the first 2 infusions, the tests listed in 7.2.1 and 7.2.4 will also be obtained pre each infusion, and at 1, 2, 4, and 6 weeks post each infusion. Follow up will then continue at 3, 6, 9 and 12 months after the last infusion. No study specific blood tests will be done after two years (if the patients have had additional injections) but we will continue to follow patients clinically once a year for up to 4 additional years (total of 5 years follow-up) to evaluate long term disease responses.

- 7.3.6 Other Tissues: Should the patient undergo a tumor biopsy at any time while they are on study, a sample of this will be used to assess the tumor antigen expression profile.

TACTIC

Version 1.0 6/17/2016
Version 1.1 8/12/2016

Version 1.2 11/3/2016
Version 2.0 3/20/2017

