- g- Should the patient undergo a tumor biopsy at any time on the study, a sample will be used to determine the tumor antigen expression profile per section 7.2.6
- h- Adverse events are assessed throughout the clinical safety monitoring timeframe
- i- Time point for evaluation clinical efficacy, and eligibility for additional doses per section 5.2

TACTIC

Version 1.0 6/17/2016
Version 1.1 8/12/2016

Version 1.2 11/3/2016
Version 2.0 3/20/2017

Version 3.0 6/28/2017
Version 3.1 7/24/2017

Version 3.2 11/16/2017
Version 4.0 12/03/2018

Version 4.1 7/24/2019

Additional Treatment

Study Procedure	Treatment									Follow-Up			
	Day 0	Wk 1	Wk 2	Wk 4	Wk 6	M 3	M 6	M 9	M 12	Y 2	Y 3	Y 4	Y 5
STUDY DRUG ADMINISTRATION													
mTAA CTL infusion	X												
DATA/TESTS/SPECIMENS TO BE OBTAINED													
Concomitant Medications	X												
PE	X												
Hx	X		X	X	X	X	X	X	X	X	X	X	X
Pregnancy Test	X												
Blood Tests [Hematology, Comprehensive Metabolic Panel] ^a	X												
Imaging studies ^b					X								
Immune function studies ^c	X	X	X	X	X	X	X	X	X				
TCR deep-sequencing ^d													
Tumor Biopsy ^e													
DATA REVIEW													
AE Assessment	X ^f												
Response Assessment					X ^g								
Follow-up						X	X	X	X	X	X	X	X
Follow-up Cancer													
Follow-up Pregnancy													
Relapse and Progression Assessment													
Death													

a- Hematology labs for CBC with differential WBC count; Clinical chemistry panel includes sodium, potassium, carbon dioxide, chloride, blood urea nitrogen, creatinine, total bilirubin, alkaline phosphatase, aspartate transaminase, alanine transaminase)

b- Imaging studies are not required with additional doses but if performed the data will be collected.

c- Blood will be used for immune function assays including ELISPOT and cytotoxicity assays

d- If required, TCR deep-sequencing will be performed to compare the infused product with the patient's peripheral blood per section 5.2

e- Should the patient undergo a tumor biopsy at any time on the study, a sample will be used to determine the tumor antigen expression profile per section 7.2

f- Adverse events are assessed throughout the clinical safety monitoring timeframe

g- Data pertaining to clinical efficacy and safety monitoring will be obtained 6 weeks after the final injection per section 9.2

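### No systematic toxicity collection is planned beyond 6 weeks after the last dose, and the window for late serious events is not stated, although infused cells are tracked to 12 months

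*Combined protocol and SAP*

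**What the plan says.** **Collection window.** Section 12.3.3: "Data on adverse experiences/toxicities regardless of seriousness, must be collected for documentation purposes only for 6 weeks after the last dosing of study drug/biologic". Section 5.2: "A time period of 6 weeks post the 2nd infusion will constitute the time for clinical efficacy and safety monitoring". Both study calendars in 7.4 mark AE assessment once, at Day 0, with a footnote (h in the main calendar): "Adverse events are assessed throughout the clinical safety monitoring timeframe". Under 10.1.3, collection stops earlier if the patient starts treatment for progression.

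**Serious events and the halt rule.** Section 12.3.4: "Serious adverse events will be collected as per SOP J 02.06.XX". No time window is given. The 9.4 rule (two patients with possibly related grade 4 events) has no time limit either.

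**Persistence.** Section 7.3.4 ends its immune sampling schedule at "6 weeks and 3, 6, 9, and 12 months following the 2nd infusion". Section 7.1 adds: "If persistence of cells is noted at the 12 month visit, additional follow-up will added".

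**Named risk.** Section 3.1(iv), on over-expressed antigens including Survivin, one of the five targets: "T cells targeted to these antigens carry the risk of inducing collateral damage to normal tissues co-expressing the antigen". It also says that clinical safety data for these antigens are limited.

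**Later visits.** Section 7.2 takes a complete history at 3, 6, 9 and 12 months and then yearly. Neither calendar marks a physical examination, safety laboratory test or AE assessment after week 6.

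**The concern.** The product is living cells. The protocol looks for their survival and for epitope spreading (5.2), and 3.3 reports spreading to non-targeted antigens in the lymphoma patients. Harm to normal tissue need not appear within 6 weeks of an infusion, yet systematic collection ends there.

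Two things are at stake. First, sections 3.4 and 9.0 present the trial as a test of safety, but the 9.2 safety summary would contain no systematically collected toxicity beyond that point. A blank could not be told apart from an absence of events, because no denominator is defined. Second, 12.3.3 applies its limit whatever the seriousness, while 12.3.4 sends serious events to a separate SOP. A reader cannot tell from the protocol how a late serious or grade 4 related event would come to light for the 9.4 count.

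**Working it through.** **1. The plan's own figures.** No stated figure depends on the collection window. The patient numbers used below do reproduce. The exact two-stage calculation (continue with at least 1 of 9, success with at least 3 of 17) gives alpha 0.0466, power 0.9045, early stopping probability 0.630 and expected size 11.96 at a 5% rate. Accrual is 17/(1 − 0.20) = 21.25, rounded up to 22.

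**2. Share of monitoring covered, two doses.** Inputs: doses 4 weeks apart (6.2), collection for 6 weeks after the last dose (12.3.3), immune sampling to 12 months after dose 2 (7.3.4).
- Collection ends at week 4 + 6 = 10 after dose 1.
- Sampling ends at about week 4 + 52 = 56.
- Covered: 10/56 = 18%. Not covered: 56 − 10 = 46 weeks.

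**3. Re-dosed patients.** Up to 6 more doses are allowed, the first no sooner than 6 weeks after dose 2 (week 10), at least a month apart (6.2). For all 8 doses at the shortest spacing:
- With 4-week months, the last dose is at week 10 + 5 × 4 = 30 and collection ends at week 36.
- With calendar months, the last dose is at about week 31.7 and collection ends at about week 37.7.
- The additional-treatment calendar continues sampling to 12 months after the last infusion, so the share is 36/(30 + 52) = 44%. The uncovered stretch is still 52 − 6 = 46 weeks.

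**4. Halt rule, conditional illustration.** Let q be the per-patient rate of possibly related grade 4 events and f the share of them that becomes known. The documents give neither; both are assumptions. P(rule met) = 1 − (1 − qf)^N − N·qf·(1 − qf)^(N−1).

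| N | q | f = 1 | f = 0.5 | f = 0.25 |
|---|---|---|---|---|
| 22 | 5% | 0.30 | 0.10 | 0.03 |
| 22 | 10% | 0.66 | 0.30 | 0.10 |
| 22 | 20% | 0.95 | 0.66 | 0.30 |
| 17 | 10% | 0.52 | 0.21 | 0.07 |
| 17 | 20% | 0.88 | 0.52 | 0.21 |

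If the SOP captures late grade 4 events, the f = 1 column applies and nothing is lost. The table shows only why the SOP's window matters.

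**5. What late collection could show.** With zero events in n patients, the one-sided upper 95% bound is 1 − 0.05^(1/n).

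| n | Upper bound |
|---|---|
| 22 | 12.7% |
| 10 | 25.9% |
| 7 | 35% |
| 5 | 45.1% |

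The value for 22 is a best case: every accrued patient followed to month 12 with no other therapy. As a rough guide to who remains, the 30% target benefit rate gives 0.30 × 17 = 5.1 to 0.30 × 22 = 6.6 patients with benefit at week 10. At the 5% null rate it is about one (0.05 × 22 = 1.1).

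**The case against.** The case for leaving the plan alone is substantial.

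- **The window is deliberate.** It recurs in 5.2, 7.4, 8.0, 9.2 and 12.3.3, and section 2 lists only efficacy and survival. This stands: it is a design choice, and no stated result is wrong because of it.
- **Other provisions reach past 6 weeks.** Section 10.1.1 follows related toxicity of grade III or higher to resolution or the off-study date, and 11.0 keeps adverse event records on all patients. These stand as far as they go. The first follows toxicity already found; the second keeps records. Neither schedules a search for new late events.
- **Unseen documents may fill the gap.** Section 12.3.3 cites two further SOPs, section 14.0 cites monitoring plans, and the 6-week sentence could be read as a minimum duty. This is possible, so one cannot say that late events will go uncollected, only that the protocol does not provide for them.
- **The risk may be small.** Section 3.3 reports no adverse events in 18 lymphoma patients, 3.5 lists only cytokine release syndrome, and 3.1(iv) also allows that efficacy without toxicity is possible. That is fair; normal-tissue damage is one risk, tied to one of five targets.

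A reader might also infer three stronger points that the text does not support. The first is that the plan expects cells to persist to 12 months: 7.1 makes persistence a condition, and sampling tests it. The second is that late toxicity is neither reported nor counted in the halt rule: 12.3.4 provides for serious events, and 9.4 has no time limit, so a known late related grade 4 event counts. The third is that the 3 to 12 month visits serve disease response only: 7.1 attaches that purpose to the four additional years after month 12.

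**Conclusion.** The point holds as a gap in prescribed data collection. After 6 weeks from the last dose, or once therapy for progression starts, the protocol schedules no toxicity assessment and states no window for late serious events. Late non-serious related toxicity has no planned route into the safety summary. Ascertainment of late grade 4 related events depends on an SOP that the documents do not contain.

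For a two-dose patient, 18% of the monitored period is covered; the share rises with re-dosing, but about 46 weeks after the last dose stay uncovered. This assumes that monitoring means the scheduled 12 months of immune sampling. Any loss of halt-rule sensitivity is conditional on the SOP and on assumed q and f, and is not a finding. The efficacy design is unaffected. The gain from the change is real but modest, because few patients are likely to remain free of other therapy.

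**What to change.** - **12.3.3 and footnote h (with its counterpart in the additional-treatment calendar):** at the existing 3, 6, 9 and 12 month visits, counted from the last infusion, record new events considered at least possibly related, with grade, until other cancer therapy starts.
- **12.3.4:** state the collection window for serious events, and say whether the 6-week limit applies to them.
- **9.2:** report these events separately from those within 6 weeks of the last dose, with the number of patients still under collection as denominator and an exact upper bound.
- **Consistency:** reconcile 7.1, 9.4, 10.1.3, 12.3.3 and 12.3.4, so that the end of collection and the events reaching the 9.4 count can be read from the protocol itself.

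The cost is protocol wording and one short form at four visits already held, with no extra visit or test. The drawbacks are less certain attribution at later times, which separate reporting makes visible, and wide bounds from small numbers. Events detectable only by laboratory test would still be missed unless a test were done for another reason.
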